1.1 Study design

This is a single arm, prospective, multicentre and open-label, 96-week study to evaluate the treatment effectiveness of ofatumumab (OMB157) in subjects with relapsing MS transitioning from any fumarate-based RMS approved therapy, such as DMF or DRF, or fingolimod due to breakthrough disease activity. A total of approximately 555 eligible subjects will receive open-label ofatumumab 20 mg s.c. every 4 weeks (after an initial loading regimen of three weekly 20 mg doses in the first 14 days).

The study is divided into three parts: Part 1 - Screening period, Part 2 - Treatment period, Part 3 - Safety follow-up.

Figure 1-1 Study Design

Transition period is described in protocol Section 6.6.1.

Part 1 - Screening (and transition) period

The Screening period can last up to 60 days and consists of two sections; namely Screening section and Baseline section. The Screening period will include the transition period (see

protocol Section 6.6.1 for details around subjects transitioning from either a fumarate therapy or fingolimod as per clinical practice). Baseline section can last up to the point of first study drug administration (Day -7 to Day 1). Participant eligibility will be determined based on the Screening and Baseline assessments.

Part 2 - Treatment period

Treatment period will consist of an initial induction phase (Week 1 to Week 4) with 20 mg s.c. of atumumab during visits at Day 1, Day 7 and Day 14 followed by a monthly maintenance dose regimen of 20 mg s.c. of atumumab every 4 weeks starting at Week 4. During the treatment period, the subjects will have the assessments as per Table 8-1 in the protocol. All visits should be performed in the morning whenever possible to reduce the impact of fatigue on the scheduled assessments.

Part 3 - Safety follow-up period

Safety follow-up:

- The Safety follow-up (FU) period will be applicable for the following subjects:
 - Subjects who complete the Treatment period on the study drug and do not continue ofatumumab treatment (either commercial ofatumumab via prescription or via Post-Trial Access mechanisms*)
 - Subjects who prematurely discontinue study drug
- All Safety FU visits must be scheduled relative to the End of Study (EOS) Visit.

*Post-Trial Access

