2.1.2 Visit Windows

2.1.2.1 Visit windows for treatment epoch

Visit-windows will be used for both efficacy and safety data summaries by visit. Visit windows define a time period "around" the targeted visit date as defined in the evaluation schedule of the clinical study protocol. Visit-windows are non-overlapping, and defined without gaps between consecutive visit windows. The width of visit windows may vary over the course of the study period.

Baseline assessments are defined in Section 2.1.1 and do not require a visit window.

The purpose of visit windows is to analyze data based on the actual study days (rather than "nominal" visits). E.g., if a subject's Month 1 visit is delayed; it is possible that the Month 1 data be re-aligned to visit-window Month 2 and be summarized under Month 2.

- For efficacy analyses all nominal visits (i.e. excluding unscheduled visits) will be mapped into one of the defined visit-windows. Note: for the derivation of disability worsening or improvement all visits (scheduled and unscheduled) need to be considered before the worsening or improvement can be confirmed. Similarly, for No Evidence of Disease Activity (NEDA-3), all visits (scheduled and unscheduled) need to be considered.
- For safety analyses all visits (scheduled and unscheduled) will be mapped to visit windows. Safety data from unscheduled visits may be reported separately if applicable.

It is possible that more than one assessment of a subject fall into a particular visit-window. Section 2.1.2.3 deals with the statistical approaches to handle multiple visits in a given visit window.

Tables displaying summary statistics "by visit" will also use the term visit-window as column header; this is to remind the reviewer that multiple assessments of a participant might be summarized. Below tables provide visit-windows definitions for applicable parameters.

Table 2-3 Visit-windows for EDSS / T25FW / 9HPT

Visit-window	Start day	Target day	End day
Week 24	1	168	252
Week 48	253	336	420
Week 72	421	504	588
Week 96	589	672	762

Table 2-4 MRI

Visit-window	Start day	Target day	End day
Week 24	2	168	252
Week 48	253	336	504
Week 96	505	672	762

Table 2-5 Visit-windows for vital signs*

		 			
Visit-window	Start day	Target day	End day		
Week 4	1	28	98		
Week 24	99	168	252		
Week 48	253	336	420		
Week 72	421	504	588		
Week 96	589	672	762		

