2.14 Other Exploratory analyses

Following exploratory endpoints will be analyzed as part of CSR based on FAS population.

2.14.1 6-month Confirmed Disability Worsening (6mCDW)

A 6-month confirmed disability worsening (6mCDW) is defined as an increase from baseline in EDSS sustained for at least 6 months. This means that after a scheduled or unscheduled visit at which the participant fulfills the disability worsening criterion as defined in Table 2-16, all EDSS assessments (scheduled or unscheduled) need to also fulfill the worsening criteria until the worsening ("the event") can be confirmed at the first scheduled visit that occurs in the absence of (confirmed or unconfirmed) relapse 6 months/166 days after the onset of the worsening, or later.

In the time to event (6mCDW) analysis, time will be calculated as (the date of EDSS assessment at onset of the event – date of first administration of study drug+1) for patients with the events. Censoring occurs in those participants who did not experience an event up to the analysis cutoff date (i.e. end of treatment epoch date), this includes participants who had a "tentative" disability worsening that could not be confirmed due to an early discontinuation or any another reason.

The censoring time is calculated as (the date of last EDSS assessment up to analysis cutoff date – date of first administration of study drug+1). Additional details are provided in footnote of Table 2-16.

Table 2-16 Criterion for disability worsening based on change in EDSS score

Total EDSS at baseline*	"Disability worsening" criterion
0	≥ +1.5
0.5 to 5	≥ +1
≥5.5	≥ +0.5

A 6-month confirmed disability worsening can have an onset at any scheduled or unscheduled visit if the disability worsening criterion is met. A disability worsening event can only be confirmed at a scheduled visit in the absence of (confirmed or unconfirmed) relapse if, over a period of 6 months (≥166 days=6*30-14 [visit window]) time interval, all assessments meet the worsening criterion.

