2.14.6 Change from baseline in T2 lesion volume

Raw T2 lesion volume and change from baseline in T2 lesion volume will be summarized by visit window. The mixed model for repeated measures (MMRM) model will be fitted, using log-transformed change from baseline T2 lesion volume as the outcome, adjusting for last prior DMT and visit as factors, log-transformed baseline T2 lesion volume, baseline EDSS and subject's age at baseline as continue covariates. Unstructured correlation matrix will be specified within the model. Estimates for each visit window, as well as 95% CI and p-values will be given. This analysis will also be repeated by last prior DMT. In case model has convergence issues, the following actions will be taken: 1) Drop age; 2) Change the covariance structure from unstructured to Autoregreesive(1). Details of MMRM model and SAS codes will be provided in Section 5.4.4.

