2.14.8 Proportion of subjects without MRI activity

The proportion of subjects free of Gd-enhanced T1 lesions (in this scan) at Week 24, Week 48 and Week 96 will be summarized.

The proportion of subjects free of Gd-enhanced T1 lesion (all post-baseline scan) will be summarized. This analysis should only include subjects with MRI results at Week 24, Week 48 and Week 96.

The proportion of subjects free of new or enlarging T2 lesion (all post-baseline scan) will be summarized. This analysis should only include subjects with MRI results at Week 24, Week 48 and Week 96.

MRI scans conducted while on steroid should be kept in this analysis. Above analyses will be repeated by last prior DMT.

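### The AR(1) fallback for the T2 lesion volume and NfL repeated-measures models assumes one variance at all visits, so per-visit intervals would be miscalibrated if the spread differs by visit

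*SAP*

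**What the plan says.** SAP 2.14.6 models log-transformed change from baseline in T2 lesion volume. Last prior DMT and visit are factors; log baseline volume, baseline EDSS and age are covariates. On covariance it says "Unstructured correlation matrix will be specified within the model", and on output "Estimates for each visit window, as well as 95% CI and p-values will be given". If convergence fails, the actions are "1) Drop age; 2) Change the covariance structure from unstructured to Autoregreesive(1".

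SAP 2.14.10 gives the same two-step fallback for serum NfL, again with an estimate, 95% CI and p-value per time point. Both models are repeated by last prior DMT.

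The MRI visits are Weeks 24, 48 and 96 (Table 2-4, target days 168, 336 and 672). Section 2.14.8 uses the same schedule, with results "at Week 24, Week 48 and Week 96 will be summarized". For NfL, Table 2-9 defines nine windows, from Week 4 to Week 96.

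The code is deferred: "Details of MMRM model and SAS codes will be provided in Section 5.4.4". In the public text that section has a title but no code. The visible SAP text mentions no heterogeneous variances and no robust standard errors for the fallback.

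**The concern.** An unstructured matrix estimates a separate variance at each visit. AR(1) as named has two parameters: one variance common to all visits and one correlation between adjacent visits. The SAP's output is visit by visit, so the common-variance assumption acts directly on what is reported. Where the true spread exceeds the pooled value, the standard error is too small and the p-value too optimistic; where it falls short, the interval is too wide.

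The order of steps adds to this. Dropping age removes one mean parameter and no covariance parameter. It therefore changes the adjusted estimate while leaving the covariance matrix, the more likely source of non-convergence, as large as before.

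**Working it through.** The documents state no figure for this point, so there is nothing to reproduce.

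**Inputs from the documents.** There are about 555 subjects (SAP 1.1), three MRI visits (Table 2-4) and nine NfL visits (Table 2-9).

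**Covariance parameters.** With k visits, unstructured has k(k+1)/2, heterogeneous AR(1) has k+1, and AR(1) has 2.
- T2 volume, k = 3: 6, 4 and 2.
- NfL, k = 9: 45, 10 and 2.

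**Assumptions, none of them in the documents.** SD ratios across Weeks 24:48:96 are as tabulated. The 24-week correlation is 0.6 to 0.9, and correlation either decays with time or is constant. Data are complete, or 15% are missing by Week 96 (5% with Week 24 only, 10% with Weeks 24 and 48 only).

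**Hand approximation.** With complete data, the true SE at visit j is σ_j/√n. AR(1) replaces σ_j by a common s, where s² is close to the mean of the visit variances. Then

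ratio_j = s/σ_j, and coverage_j = 2Φ(1.96 × ratio_j) − 1.

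For 1:1.25:1.5, s² = (1 + 1.5625 + 2.25)/3 = 1.604 and s = 1.267. At Week 96 the ratio is 1.267/1.5 = 0.844 and coverage is 2Φ(1.655) − 1 = 90.2%. At Week 24 the ratio is 1.267 and coverage is 98.7%. The same steps give the other rows.

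| SD ratio | s² | Week 96 ratio | Week 96 coverage | Week 24 coverage |
|---|---|---|---|---|
| 1:1:1 | 1.000 | 1.000 | 95.0% | 95.0% |
| 1:1.1:1.2 | 1.217 | 0.919 | 92.8% | 96.9% |
| 1:1.25:1.5 | 1.604 | 0.844 | 90.2% | 98.7% |
| 1:1.5:2 | 2.417 | 0.777 | 87.2% | 99.8% |

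**Full calculation.** The large-sample limit of a likelihood-fitted AR(1), compared with the true (sandwich) SE over all correlation and missing-data assumptions above, gave:
- Week 96: 92.5–92.9%, 89.7–90.4% and 86.5–87.7% for the three growing-variance patterns. Two-sided 5% tests would then run at about 7%, 10% and 13%.
- Week 24: 96.8–97.0%, 98.6–98.7% and 99.7–99.8%.

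**Simulation check.** REML with N = 555, 24-week correlation 0.8, 15% missing and 600 replicates gave Week 96 coverage of 94.7% (1:1:1), 89.2% (1:1.25:1.5) and 88.3% (1:1.5:2). The simulation error at 90% coverage is √(0.9 × 0.1/600) = 1.2 percentage points.

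**Effect of spacing alone.** The MRI gaps are 24 and 48 weeks. With equal variances, per-visit coverage stays at 94.8–95.1%. A Week 96 minus Week 24 contrast would cover 94.5–94.9% if correlation decays with time and 98.5–99.3% if it is constant. The visible text of 2.14.6 does not list that contrast as an output.

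**The case against.** The strongest objection is that the decisive code cannot be seen. Section 5.4.4 may already use heterogeneous variances or empirical standard errors, and the SAP's document history shows that sample code there was revised in Amendment 4. This stands, and it makes the recommendation conditional. It does not remove the point, because the fallback as worded in 2.14.6 and 2.14.10 names AR(1) without qualification.

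A second objection is that the fallback may never be used. It requires the unstructured fit to fail, and AR(1) comes only after age is dropped. With three visits and 6 covariance parameters in about 555 subjects, failure for T2 volume overall is unlikely. NfL, with 45 parameters, and the smaller repeats by prior DMT are more plausible triggers. A reader might infer that the intervals will be wrong; the documents support only that they could be.

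A reader might also blame the unequal scan spacing. It breaks the AR(1) pattern but barely moves the per-visit intervals. For NfL only the first of eight gaps differs (8 weeks, then seven of 12).

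Dropping covariates in a stated order is also how 2.14.4 and 2.14.5 handle convergence, and baseline volume, EDSS and prior DMT stay in the T2 model. No loss from omitting age has been shown, so that part concerns order rather than bias.

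Finally, the planned descriptive summaries by visit include standard deviations, so a reader could see unequal spread. That would reveal the problem without correcting the intervals.

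**Conclusion.** The point holds as a minor one. If the unstructured fit fails and a homogeneous AR(1) with model-based standard errors is used, per-visit inference is right only when the spread of log change is about equal across visits. Under the assumed patterns of growing spread, Week 96 coverage falls to about 93%, 90% or 87%, and Week 24 intervals are conservative. With equal spread there is no material effect. If spread shrank over time, the direction would reverse.

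These figures are for the three MRI visits; none was calculated for NfL. A steeper assumed pattern would give a lower figure, but nothing in the documents supports choosing one, so no single coverage value should be quoted as the expected loss. The endpoints belong to the exploratory group introduced by "Following exploratory endpoints will be analyzed as part of CSR based on FAS population", and the primary ARR analysis uses a different model and is unaffected.

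**What to change.** In SAP 2.14.6 and 2.14.10, unless the Section 5.4.4 code already does this:

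1. Change the covariance structure before dropping age.
2. Replace homogeneous AR(1) with a fallback that keeps visit-specific variances, such as heterogeneous AR(1). It needs 4 parameters for T2 volume and 10 for NfL. It is still indexed by visit, but the check shows that spacing matters little for per-visit intervals. Heterogeneous Toeplitz is a weaker first step for T2 volume, because with three visits it saves only one parameter against unstructured (5 against 6) and is also indexed by visit.
3. Use empirical (sandwich) standard errors whenever the final structure is not unstructured.

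If the code already contains these options, state them in the two sections. The cost is a sentence in each section and a code option, slightly more covariance parameters than AR(1), and possibly wider late-visit intervals. Nothing changes if the unstructured model converges.

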2.14.7 Proportion of subjects with No Evidence of Disease Activity (NEDA-3)

NEDA-3 is a composite of three related measures of disease activity: (i) no relapses; (ii) no 6-month confirmed disability worsening (6mCDW); (iii) no MRI activity (new of enlarging T2 lesions or Gd-enhancing lesion).

NEDA-3 will be set to "No" if at least one of the following conditions is met; otherwise NEDA-3 will be set to "Yes".

- 6mCDW event
- Confirmed relapse
- ≥1 Gd-enhancing T1 lesions
- ≥1 new/enlarging T2 lesions
- Discontinued from study drug due to either "death" or "lack of efficacy"

Proportions of subjects after 96 weeks that meet the criteria of NEDA-3 will be summarized descriptively by last prior DMT (fumarates vs. fingolimod), along with 95% CI.

NEDA-3 will also be summarized by year (use Day 365.25 as the cut-off of Year 1 and Year 2), as well as by year and by last prior DMT, along with corresponding 95% CI. In addition, each NEDA-3 components (Gd-enhancing T1 lesions, new and enlarging T2 lesions, MRI lesion activity, confirmed relapses, 6mCDW, discontinued from study drug due to either death or lack of efficacy) will be summarized by year.

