⁸ Remote contact with subjects by site staff around the time of administration of ofatumumab self/home-injection. The contact should query about any new or worsening symptoms warranting an unscheduled visit, compliance with study treatment, injection reactions, results of home pregnancy testing and compliance with contraception requirements (when applicable). Method of contact can be via telephone, email or text message depending on the preference of each subject.

⁹ Restrictions may apply to MRI concerning steroid use, please refer to Section 8.3.4.

¹⁰ Screening MRI should be completed once all other screening eligibility assessments have been completed and confirmed to meet eligibility criteria

¹¹ MRI scan at the EOS visit is needed if there was no MRI scan in the previous 3 months.

Period	Scre	ening	Treatment												
Visit Name	Screening	Baseline	Visit 12	Visit 2 (Remote contact Visit) ³	Visit 3 Week 2 ²⁴	Visit 4 Week 4	Visit 5 Week 8 ²⁴		Visit 7 Week 24	Visit 8 Week 36 ²⁴	Visit 9 Week 48	Visit 10 Week 60 ²⁴	Visit 11 Week 72	Visit 12 Week 84 ²⁴	EOS/Visit 13 Week 96 ⁴
Visit Numbers ¹	1	20	100	110	120	130	140	150	160	170	180	190	200	210	220
Days	-60 to -8	-7 to 1 (Prior to 1 st dose/visit 1 start)	1	7 ±1	14 ±1	28 ±1	56 ±7	84 ±7	168 ±14	252 ±14	336 ±14	420 ±14	504 ±14	588 ±14	672 ±14

¹² Timed 25-Foot Walk, Nine Hole Peg Test

- via the CCI application will be conducted in countries where applicable languages are available. Data is collected continuously throughout the study. CCI should be dispensed at Baseline Visit, and given to the patient a minimum of 7 days prior to planned first study drug dose, and returned at EOS/Visit 13. On the days of the scheduled site visits, the CCI assessments will be performed under the supervision of trained site staff.
- ¹⁶ Subject to return CCI for data download and transfer. It's necessary to obtain CCI data at least 1 week before Visit 1. These data will be considered as CCI baseline data. Refer to Section 8.5.1.6 for more information.
- ¹⁷ Vital signs should be obtained 30-60 minutes before Day 1 s.c. injection (if premedication is administered, pre-injection vital signs should be obtained before premedication is administered), and again approximately 60 minutes post Day 1 s.c. injection

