- In case the investigator deems the benefit-risk of continuing study treatment to be unfavorable or if the subject does not wish to continue study treatment, the subject will be discontinued from the study and will enter the Safety Follow-up period (Table 8-2). The investigator will be notified by the Sponsor when a subject meets the criterion for 6mCDW.

If discontinuation of study drug occurs, the investigator should make a reasonable effort to understand the primary reason for the subject's premature discontinuation of study drug and record this information.

Subjects who discontinue study drug or who decide they do not wish to participate in the study further should NOT be considered withdrawn from the study UNLESS they withdraw their consent (see Section 9.1.2). Subjects that discontinue treatment should complete the EOS visit and move to the Safety Follow-up as per Table 8-2. If they fail to return for these assessments for unknown reasons, every effort (e.g. telephone, e-mail, letter) should be made to contact the subject/pre-designated contact as specified in Section 9.1.3. This contact should preferably be done according to the study visit schedule.

If the subject cannot or is unwilling to attend any visit(s), the site staff should maintain regular contact with the subject, or with a person pre-designated by the subject. This contact should preferably be done according to the study visit schedule for up to 6 months post last study drug administration.

After study drug discontinuation, at a minimum, in abbreviated visits, the following data should be collected at clinic visits or via telephone/email contact:

- New / concomitant treatments
- Adverse Events / Serious Adverse Events

The investigator must also contact the IRT to register the subject's discontinuation from study drug.

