1.2 Study objectives and endpoints

Table 1-1 Objectives and Endpoints

Objective(s)	Endpoint(s)		
Primary objective(s)	Endpoint(s) for primary objective(s)		
Demonstrate the effectiveness of ofatumumab 20 mg s.c. administered every 4 weeks in subjects with relapsing forms of MS who had breakthrough disease on fumarates or fingolimod	Annual relapse rate (ARR, based on confirmed relapses) measured over the 96 weeks		
Secondary objective(s)	Endpoint(s) for secondary objective(s)		
Evaluate the safety of ofatumumab 20 mg s.c. administrated every 4 weeks in subjects with relapsing forms of MS who had breakthrough disease on fumarates or fingolimod	 Proportion of subjects with adverse events, including injection related reactions Proportion of subjects with laboratory or vital signs results meeting abnormal criteria The proportion of subjects discontinuing treatment due to insufficient effectiveness (lack of efficacy) or tolerability/safety reasons 		
Exploratory objective(s)	Endpoint(s) for exploratory objective(s)		
Demonstrate effectiveness of ofatumumab 20 mg s.c. administered every 4 weeks	 Change from Baseline during the treatment period, of the following Assessments: EDSS Timed 25-Foot Walk (T25FW) Nine-Hole Peg Test (9HPT) Low Contrast Visual Acuity (LCVA) T2 lesion volume Time to 6-month Confirmed Disability Worsening (6mCDW) based on EDSS Time to a 6-month confirmed cognitive decline (6mCCD), defined as a 4-point worsening on Number of T1 Gd+ lesions per scan Number of new or enlarging T2 lesions on MRI per year (annualized T2 lesion rate) Proportion of patients without MRI activity Proportion of subjects with No Evidence of Disease Activity (NEDA-3) as per protocol defined events during a 96-week period 		
Explore patient reported outcomes in subjects treated with ofatumumab 20 mg s.c. administered every 4 weeks	Change from Baseline during the treatment period of the following Assessments: The impact of MS disease as measured by the CCI CCI CCI CCI CCI CCI CCI CCI		
Explore Neurofilament (NfL) light chain as a biomarker for MS in terms of prognosis and disease activity monitoring	Change from baseline in serum NfL light chain concentration		

Objective(s)	Endpoint(s)			
• Explore the utility of using the application	Adherence to Classessments quantified as compliance level (%), which will be measured in terms of Classessments and other assessments performed in the study CCI includes the following: CCI CCI CCI CCI CCI CCI CCI C			

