2.2 Analysis sets

The Full Analysis Set (FAS) comprises all subjects to whom study drug has been assigned and who received at least one dose of study drug. The FAS will be used for the summary of demography and baseline characteristics as well as for all efficacy analyses except CC

The Safety Set (SAF) includes all subjects who received at least one dose of study drug. The SAF will be used for all safety analyses.

Please refer to appendix Table 5-2 for subjects to be excluded from analysis.

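### SAP 2.14.7 counts every treated patient with no recorded event as NEDA-3 Yes, so event-free early leavers and patients with missing scans enter the 96-week proportion as disease-free

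*SAP*

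**What the plan says.** - **Endpoint.** SAP Table 1-1 lists "Proportion of subjects with No Evidence of Disease Activity (NEDA-3) as per protocol defined events during a 96-week period".
- **Rule.** SAP 2.14.7 classifies a patient as No "if at least one of the following conditions is met; otherwise NEDA-3 will be set to" Yes. The five conditions are a 6-month confirmed disability worsening (6mCDW), a confirmed relapse, a Gd-enhancing T1 lesion, a new or enlarging T2 lesion, and stopping study drug for death or lack of efficacy. The section has no not-evaluable category, minimum follow-up or required scan.
- **Population.** SAP 2.14: "Following exploratory endpoints will be analyzed as part of CSR based on FAS population". By SAP 2.2 that set "comprises all subjects to whom study drug has been assigned and who received at least one dose of study drug".
- **After stopping drug.** Protocol 9.1.1: "Subjects that discontinue treatment should complete the EOS visit and move to the Safety Follow-up as per Table 8-2". Table 8-2 lists relapse and EDSS but no MRI.
- **Exit scan.** Protocol Table 8-1, footnote 11: "MRI scan at the EOS visit is needed if there was no MRI scan in the previous 3 months".
- **Unconfirmed worsening.** SAP 2.14.1 censors a tentative worsening that early discontinuation leaves unconfirmed, so it does not make NEDA-3 No.
- **Visits used.** SAP 2.1.2.1 has both scheduled and unscheduled visits considered for NEDA-3.
- **By year.** "NEDA-3 will also be summarized by year (use Day 365.25 as the cut-off of Year 1 and Year 2". No denominator is given for Year 2.

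**The concern.** A patient who stops after a few months because of an adverse event, by own decision or through loss to follow-up, with nothing recorded, becomes a 96-week success. The rule reads absence of observation as absence of disease. Unscheduled visits and the exit scan catch activity only up to exit, and no MRI covers the time from exit to Week 96.

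Other parts of the SAP handle unequal follow-up. The primary analysis uses log time in study as an offset (2.5.2), and 6mCDW, a NEDA-3 component, is censored and estimated by Kaplan-Meier (2.14.1). The composite gives the same leavers full credit for 96 weeks.

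The trial has one arm, so the NEDA-3 proportion is read at face value. The comparison by last prior DMT could also shift if leaving differs between the fumarate and fingolimod groups.

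**Working it through.** The documents state no expected NEDA-3 proportion, leaving rate or missing-scan rate, so there is no plan figure to reproduce. The size below rests on assumptions.

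**From the documents:** relapse rate 0.16 per year (SAP section 3); N about 555; Day 672; scans at Weeks 24, 48 and 96; 166 days to confirm worsening.

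**Assumed:** gamma frailty for relapses, dispersion 1; lesion probability 15%, 5% and 5% at the three scans, independent; worsening 3% per year; leaving for other reasons at 2%, 5% or 10% per year; an exit MRI in 0% or 90% of leavers whose last scan is over 91 days old; activity rates unchanged after exit.

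**Step 1: true NEDA-3 under full follow-up.** 672/365.25 = 1.840 years.
- Relapse-free: 1/(1 + 0.16 × 1.840) = 0.773
- MRI-free: 0.85 × 0.95 × 0.95 = 0.767
- No confirmed worsening: exp(−0.03 × (672 − 166)/365.25) = 0.959
- Product: 0.568, or 56.8%

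**Step 2: leaving by Day 672** = 1 − (1 − r)^1.840, giving 3.6%, 9.0% and 17.6% for r = 2%, 5% and 10%.

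**Step 3: inflation** = (event-free leavers as a share of the FAS) × (share of them with a true event that was not recorded). Both shares come from simulation with at least 1,000,000 patients per run; ranges cover the two exit-MRI settings.

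| Leaving | Event-free leavers, % of FAS (of 555) | Current rule | Inflation, points | All event-free leavers set to No |
|---|---|---|---|---|
| 3.6% | 2.7–2.8 (about 15) | 57.4–57.5% | +0.6 to +0.7 | about 55% |
| 9.0% | 6.7–6.8 (about 38) | 58.3–58.5% | +1.5 to +1.7 | 51.7% |
| 17.6% | 13.0–13.4 (about 73) | 59.9–60.2% | +3.0 to +3.4 | 46.8% |

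About 22–25% of the event-free leavers have a true unrecorded event. For example, 6.7% × 0.23 = 1.5 points and 13.0% × 0.23 = 3.0 points.

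**Step 4: sensitivity at 9% and 17.6% leaving.**
- Relapses in six months of Safety Follow-up also counted: +1.1 to +1.3 and +2.2 to +2.6.
- Lower activity (relapse rate 0.10; lesions 10/3/3%): +1.2 to +2.6 across the two leaving rates.
- Higher lesion activity (35/8/8%): +1.6 to +4.0.
- Year 2 with the whole FAS as denominator: +1.2 to +2.5; with patients observed at its start: +0.4 to +0.9.

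**Step 5: sampling error.** 1.96 × √(0.57 × 0.43/555) = 4.1 points.

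**Step 6: alternatives in the same simulation.**
- Life table on the scan intervals: off by +0.1 to +0.5, or +0.1 to +0.9 if the leaving rate doubles after activity.
- Completers only: 0.0, but +1.4 to +2.9 if it doubles.
- Deleting only event-free leavers: −1.4 to −3.0.

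**The case against.** **Small and exploratory.** The inflation is below the confidence half-width, the endpoint is descriptive, and every driver except the relapse rate and N is assumed. With 4% leaving it is about half a point. The share of event-free leavers with an unrecorded event also varies, from roughly 15% to 36% across the activity scenarios. All of this stands and limits the weight of the point. It does not remove it: the error has one direction and the interval does not cover it.

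**Partial protection exists.** Stops for lack of efficacy or death are already No, unscheduled visits count, and there is an exit scan. This stands up to exit only. The statement that the rule inflates applies to its default-Yes part; the same rule also counts deaths unrelated to MS as No.

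**Redaction.** The efficacy cutoff, SAP 5.1, Table 5-2 and an exception in SAP 2.2 are not visible, so a rule there cannot be excluded. But 2.14 restates the FAS and 2.14.7 cross-refers to no other rule.

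**A stronger size.** A reader might take the gap to the all-No count as the bias: 8 points at an assumed 10% leaving with 80% of leavers event-free (0.10 × 0.80). That is a worst-case bound. It would be the bias only if every event-free leaver truly had an event.

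**An MRI error.** SAP 2.14.8 says of its two all-scan summaries: "This analysis should only include subjects with MRI results at Week 24, Week 48 and Week 96". A patient with a known lesion and a missing scan is therefore excluded, and a reader might infer upward bias. The documents do not support that. Lesion-free patients with a missing scan are excluded too, and the denominator is openly stated. With a true lesion-free share f = 0.767 and missing-scan shares m, the estimate is f(1 − m_free)/[f(1 − m_free) + (1 − f)(1 − m_lesion)]. The bias is 0 at 10%/10% (free/lesion), −1.0 at 15%/10%, +1.0 at 10%/15% and +2.0 at 10%/20%. Its direction is not fixed.

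**Conclusion.** The point holds for NEDA-3. The visible text is a closed rule that makes event-free early leavers and patients with missing scans count as disease-free over 96 weeks. Against 96-week status under full follow-up, the default-Yes part inflates the proportion by about 0.6, 1.5 or 3 points at assumed 4%, 9% or 18% leaving. This assumes that activity rates do not change after exit, and that no hidden section already holds a different rule.

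The effect is modest, below the 4.1-point half-width, and confined to an exploratory endpoint. A reader might infer that the trial's main conclusion is at risk. It is not, because the primary annualized relapse rate test does not use this rule. The all-scan MRI summaries in 2.14.8 are a secondary matter for an optional sensitivity analysis.

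**What to change.** In SAP 2.14.7:

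1. Count every observed event as No, whatever the later follow-up.
2. Treat event-free patients with incomplete follow-up or scans as not evaluable from that point, not as Yes.
3. Estimate the 96-week proportion with a method that uses partial follow-up, for example a life table on the scan intervals. Do not delete only the event-free leavers, which biases the result downward.
4. Base Year 2 on patients under observation at its start.
5. Keep the current rule and the all-No bound as sensitivity analyses, and show the number of event-free patients with incomplete follow-up beside each proportion.

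If a redacted section already contains such a rule, a cross-reference is enough. Optionally, add a sensitivity analysis to the two all-scan summaries in 2.14.8 for patients with a known lesion and a missing scan.

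The cost is SAP wording and modest programming, with no new data. The downside is a slightly lower reported NEDA-3 and a remaining assumption that leaving is unrelated to activity.
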